3.2.1. Primary Immunogenicity Objective: IgG GMCs 4-weeks Post Booster

The previous pivotal Phase 3 study of PNEUMOSIL (VAC-056) in infants observed coefficients of variation (CV) that ranged from 0.89 to 1.46 for serotype-specific serum IgG antibody concentrations 4-weeks after a booster dose. Assuming the CVs for all PNEUMOSIL serotypes measured 4-weeks after booster in the current study are at most 1.5, the lower and upper 95% confidence bounds for each serum IgG GMC are expected to be at most 14% below and 16% above the observed GMC based on the study size of 220 per group (further assuming no more than 10% of subjects are non-evaluable due to loss to follow-up or other exclusions). For example, if the observed serotype-specific GMC = 1.0 µg/mL then the 95% CI is expected to be no wider than (0.86, 1.16) (Table 2). Similarly, the expected 95% bounds for descriptive GMC ratios (PNEUMOSIL versus either comparator) are expected to be no more than 19% below and

24% above the ratio. For example, if the observed GMC ratio equals 1.0, then the 95% CI is expected to be no wider than (0.81, 1.24), so long as the CV in the comparison group does not exceed 1.5.

Table 2. Expected precision of serotype-specific GMCs and GMC ratios (PNEUMOSIL vs. comparator) for a range of possible true GMCs and GMC ratios

GMC in PNEUMOSIL group	Expected 95% CI for GMC	GMC Ratio (PNEUMOSIL vs. comparator)	Expected 95% CI for GMC Ratio
0.5	0.43-0.58	0.75	0.60-0.93
		1.00	0.81-1.24
		1.33	1.08-1.67
1.0	0.86-1.16	0.75	0.60-0.93
		1.00	0.81-1.24
		1.33	1.08-1.67
3.0	2.58-3.49	0.75	0.60-0.93
		1.00	0.81-1.24
		1.33	1.08-1.67
5.0	4.29-5.82	0.75	0.60-0.93
		1.00	0.81-1.24
		1.33	1.08-1.67

3.2.2. Primary Safety Objective

With a sample size of 220 per group, there is 89% or greater chance of observing at least 1 safety endpoint (e.g., a solicited RE) which occurs with probability 0.01 or more. If no events of a specific classification occur, then the 95% upper confidence bound for the event rate will be at most 0.017.

3.2.3. Secondary Immunogenicity Objectives

The precision of IgG GMCs 4 weeks post completion of primary vaccination (V4) is expected to be as for the primary objective under the same assumptions about CV of serotype-specific IgGs and follow-up rates as previously described. The expected precision of other secondary immunogenicity objectives (IgG response rates, OPA response rates, and OPA GMTs) are as follows:

With a sample size of 220 per group (up to 10% of whom may not be evaluable), the half-width of 95% CIs for serum IgG response rates ($\text{IgG} \geq 0.35 \mu\text{g/mL}$ or $\text{IgG} \geq 1.0 \mu\text{g/mL}$) will be no more than 0.07, and the half-width of 95% CIs for differences in proportions should not exceed 0.10.

With a sample size of 50 per group (and no more than 10% excluded), the half-width of 95% CIs for OPA response rates (titer ≥ 8) will be no more than 0.15, and the half-width of 95% CIs for differences in proportions responding (PNEUMOSIL versus a comparator) should not exceed 0.21.

The VAC-056 study observed CV values that ranged from 0.97 to 2.11 for serotype-specific OPA titers measured 4 weeks after a booster dose of PNEUMOSIL in infants. Assuming the CVs for all 10 PNEUMOSIL serotypes in the current study are at most 2.11 at V4 and V6, the lower and upper 95% confidence bounds for each GMT are expected to be at most 32% below and 48% above the observed GMT based on the study size of 50 per group (assuming no more than 10% of subjects are not evaluable due to loss to follow-up or other exclusions). For example, if the observed serotype-specific GMT = 100, then the 95% CI is expected to be no wider than (68, 148). Similarly, the expected lower and upper 95% confidence bounds for descriptive GMT ratios (PNEUMOSIL versus either comparator) are expected to be no more than 42% below and 73% above the ratio. For example, if the observed GMT ratio equals 1, then the 95% CI is expected to be no wider than (0.58, 1.73), so long as the CV in the comparison group does not exceed 2.11.

Due to positive within-subject correlation among subjects contributing both V4 and V6 data, the precision of within-group booster-effects (ratios of GMCs and GMTs post-booster versus post-primary series) is expected to be at least as high as that of the between-group contrasts at V4 or V6 described above, under similar assumptions about CV and the percentage of evaluable subjects.

3.3. Randomization and blinding

After a subject is confirmed to have met all study eligibility requirements, he or she will be randomized in a 1:1:1 allocation ratio based on a pre-established randomization scheme stratified on field site, and receive the first dose of either PNEUMOSIL, Synflorix, or Prevenar 13 at 6 (+2) weeks of age (V1).

The eligible subject will be assigned the next numeric randomization ID for the given field site. Treatment assignments will be communicated to the unblinded dosing nurse via sealed, opaque, numerically numbered envelopes identified by a unique randomization ID. If a subject is given the wrong treatment at V1 due to an allocation error, the same vaccine will be administered at V3 and V5 so long as the error is identified before the timing of the next injection.

Except for staff responsible for preparing and administering study vaccines, performing vaccine accountability, and maintaining the security of the treatment assignments, all study personnel, including the Principal Investigator (PI) and the Sponsor, will remain blinded to subjects'

individual treatment assignments. All CRO personnel will also remain blinded to individual treatment assignments until the last subject completes V6, with the following exceptions: an unblinded monitor, a clinical supplies manager, a statistician implementing the interim analysis of immunogenicity objectives through V4 and any required unblinded analyses for the Data and Safety Monitoring Board (DSMB), and an Executive Secretary for the DSMB (if required). The interim analysis results shared with the Sponsor will include treatment group-level comparisons, but no information which could reveal individual treatment assignments. Unblinding at interim and final analyses will be conducted and documented in accordance with relevant CRO standard operating procedures (SOPs) and documented in the eTMF when the study is complete. Details regarding maintenance of blinding for any DSMB safety analyses are addressed in the separate DSMB Charter.

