Booster Vaccination and Follow Up: All subjects will return to clinic at 9-18 (+1) months of age for a booster vaccination of study vaccine that matches the original treatment assignment (V5). Standard EPI vaccinations based on the Gambian EPI schedule (measles-rubella vaccine, yellow fever vaccine, OPV) will be co-administered with the booster dose of study vaccine, except for subjects who receive the 9-month EPI vaccines earlier than the study booster dose due to impact of the COVID-19 pandemic. Prior to vaccination, a blood sample will be collected for immunogenicity assessments. Subjects will be evaluated at a follow-up visit 4 (+2) weeks later (V6), during which another blood sample will be collected for immunogenicity assessments. This visit will serve as the EOS visit for the subjects.

Unblinding of the CRO statistical personnel will occur after the last subject completes V4 to conduct an interim analysis of immunogenicity objectives through end of V4. The Sponsor, Principal Investigator, site team and rest of the contract research organization (CRO) personnel will continue to remain blinded to individual treatment assignments until all subjects complete Visit 6.

As previously noted, infants who are enrolled in the PNEUMOSIL and Synflorix groups will be offered a dose of Prevenar 13 outside the study after visit 6 for all study subjects have been completed and the study has been unblinded for the site team to ensure all recruited infants gain maximal long-term pneumococcal protection.

Safety Monitoring: Planned safety assessments will provide the data for active monitoring of vaccine safety during conduct of the trial through 4 weeks post the final (booster) vaccination.

Immediate solicited reactogenicity and vital signs will be assessed at 30 (+/- 10) minutes following study vaccine administration in all subjects. Severity of solicited reactions will be assessed by toxicity grading scale (see [Section 9.2.2](#)). The solicited local reactions assessed will include tenderness, erythema/redness, and induration/swelling at the study vaccine injection site. The solicited systemic reactions will include cutaneous rash, fever (based on axillary temperature), irritability, drowsiness, and decreased appetite.

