5.5. Dose Preparation and Administration

A limited number of appropriately trained, unblinded study personnel (herein referred to as unblinded personnel) will be responsible for preparing study vaccine doses in accordance with the randomly determined assignment, administering the study and other EPI vaccines, and handling all vaccine

accountability procedures. The number of unblinded personnel will remain limited, and these personnel will not participate in the other aspects of the clinical trial, to help ensure the integrity of the blind at the site. The unblinded personnel will not reveal subjects' randomization assignments to the subjects' parents, or staff associated with the Sponsor, CRO, or site. Unblinded personnel will retrieve a subject's randomization assignment after being informed by the PI that a subject is eligible for randomization. They will prepare the study vaccine based on the subject's randomization assignment in a setting distinct from the clinic staff, and then the unblinded study nurse will administer study vaccine to a subject in a separate clinic area. Vaccination will only ever take place in a clinical setting in which there is immediate access to the medical personnel (certified in pediatric life support), equipment and medications required for emergency resuscitation.

Since PNEUMOSIL, Synflorix and Prevenar 13 are suspensions containing an alum adjuvant, study vaccine must be shaken gently immediately prior to use, in order to obtain a uniform homogenous white suspension. Inspection of each vial/PFS will occur immediately prior to use. If a vial/PFS or its contents appear unusual in any way, the vial/PFS will not be used, and procedures detailed in the Study Specific Procedures (SSP) for documentation and disposal will be followed.

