7. Negative malaria parasitemia will be confirmed by RDT/blood film for malaria (generally a capillary sample will be used for this purpose).
8. Targeted PE will be performed, to confirm absence of exclusionary acute illness or abnormality of the extremities (skin and lymph nodes) targeted for vaccination.
9. A blood sample will be obtained for immunogenicity testing at V5 prior to vaccine administration.
10. After assessment of items 1-6 above, any basis for determining that an infant is a screen failure, or for withholding re-vaccination in the case of subjects returning for follow-up vaccinations (V2, V3 and V5) will be documented. Any subject who is not randomized will be referred back to their normal clinic for routine EPI vaccination.

The PI must approve the randomization of the subject, based on confirmation that the subject meets all eligibility criteria. Randomization will occur at Visit 1 using a predefined randomization scheme, with allocations occurring in a 1:1:1 ratio to PNEUMOSIL, Synflorix or Prevenar 13 and with stratification by field site. A subject's allocation will be selected in numeric order from a set of sealed randomization envelopes. The assignment will be associated with a unique randomization ID. Following assignment, the unblinded study personnel will maintain a list documenting the vaccine assigned and administered to given randomization IDs in a secure location that is not accessible to blinded study personnel. The subject will be referred to by screening number for the remainder of the study. The randomization identification (ID) will be required on select CRFs.

Once eligibility has been confirmed and randomization has taken place -- or it has been determined that a subject returning for a vaccination at Visits 2, 3 or 5 may be re-vaccinated -- unblinded study personnel will perform the following procedures in an area of the clinic that is not readily accessible to blinded study personnel:

1. Subject randomization ID will be recorded.
2. The assigned study vaccine will be administered and documented on the CRF at Visits 3 and 5 as to timing and location of administration (see Section 5.5 for details).
3. The EPI vaccines due at the given vaccination visit will be administered and documented on the IWC and CRF (see Section 5.5 for details). It will also be noted on the IWC that a pneumococcal conjugate vaccine has been given.

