9.4. Medication Errors

A medication error is any preventable event that may cause or lead to inappropriate investigational use or subject harm while the investigational product (IP) is in control of the healthcare professional, subject, or consumer. Examples of medication error that will require reporting to the Sponsor include the following:

- Administration of unassigned treatment.
- Administration of expired investigational material.
- Injection by the wrong route.

All AEs and SAEs will be handled as specified in this protocol whether or not they are associated with a medication error.

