3.8. Analysis Populations

The following analysis populations will be used when performing statistical analyses:

- **Enrolled Population** includes all screened subjects who provide informed consent, regardless of whether the subject is randomized. This population will be used to account fully for subject disposition, starting with the informed consent.
- **Safety Population** includes all subjects who were randomized, received a study vaccination, and provided post-vaccination safety data. Since all subjects are assessed for REs immediately following injection, the Safety Population will include all treated subjects unless a subject's safety data is unevaluable for some reason. Analyses based on this population will be analyzed according to actual treatment received at V1. This population will serve as the primary analysis population for study disposition, baseline demographics and medical history, as well as safety analyses.
- **The Full Immunogenicity Population (FIP)** includes subjects in the enrolled population who were randomized, received at least one study vaccination, and have post-vaccination immunogenicity measurement(s). Analyses based on the FIP will be performed according to randomized treatment assignment, regardless of any randomization or allocation errors. Results will serve as supportive analyses for the Primary and Secondary PP_IMM Population results (see below).
- **The Primary Per Protocol Immunogenicity Population (PP_IMM)** includes subjects in the FIP who received all 3 study vaccinations (including booster), contribute post-booster immunogenicity measurements, and have no major protocol deviations that are determined to potentially interfere with the immunogenicity assessment. This population (or a relevant subset of subjects contributing OPA results) will be used to assess the primary immunogenicity objective and secondary immunogenicity objectives 1, 2, and 7.
- **The Secondary PP_IMM Population** includes all subjects in the FIP who received both primary series study vaccinations, contribute immunogenicity measurements at 4-weeks post primary series and/or immediately prior to receiving the booster dose, and have no major protocol deviations that are determined to potentially interfere with the immunogenicity assessment. This population (or a relevant subset of subjects contributing OPA results) will be used to assess secondary immunogenicity objectives 3, 4, 5, and 6, as well when performing the planned interim analysis.

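### After a vaccine allocation error the SAP and the protocol lead to different products for the same child, and the analysis rules do not say how a mixed-product series is handled

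*SAP*

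**What the plan says.** **Dosing after an error.** SAP 3.3 has a specific rule: "If a subject is given the wrong treatment at V1 due to an allocation error, the same vaccine will be administered at V3 and V5", with the condition "so long as the error is identified before the timing of the next injection". It says nothing about later detection, or about an error first made at V3 or V5.

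The protocol has no rule written for an error. Its general rules all follow the assignment:
- Section 5.5 has unblinded staff "preparing study vaccine doses in accordance with the randomly determined assignment".
- Section 7.1.2 says: "The assigned study vaccine will be administered and documented on the CRF at Visits 3 and 5".
- Section 3 has all subjects return for a "booster vaccination of study vaccine that matches the original treatment assignment (V5").

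Protocol 9.4 lists "Administration of unassigned treatment" as a reportable medication error but gives no instruction for later doses.

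**Analysis.** For the Safety Population, SAP 3.8 says: "Analyses based on this population will be analyzed according to actual treatment received at V1". Protocol 12.2 says the same. The Primary PP_IMM "includes subjects in the FIP who received all 3 study vaccinations (including booster"), has post-booster results, and has no major deviation judged to interfere with the immunogenicity assessment. The Clinical Lead decides exclusions in blind review. The Secondary PP_IMM is built the same way around the two primary doses. SAP 3.8 states no grouping basis for either PP_IMM population. It groups the parent Full Immunogenicity Population (FIP) by randomized arm, whereas Protocol 12.2 groups the FIP by treatment received. The SAP appendix records that FIP change. It does not list the dosing rule of SAP 3.3 as a change.

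**The concern.** The trial describes a 2+1 series of a single product, and the analysis rules fit that situation. If a child receives more than one product, grouping by the V1 product assigns later reactions to the wrong vaccine. Solicited reactions after each vaccination are a primary safety endpoint (Protocol 2.3.1, SAP 2.2.1), and SAP 5.4.3 tabulates them dose by dose.

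For immunogenicity, the comparison most exposed is PNEUMOSIL against Synflorix for serotypes 6A and 19A, because Synflorix contains neither (Protocol 5.2.1). A child counted in the wrong one of those two arms moves these serotypes more than the others.

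**Working it through.** The dosing and grouping questions are settled by comparing text. The arithmetic only gives scale.

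**1. What each rule does to one child.** Safety grouping is by V1 product throughout.

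| Situation | Series | Solicited-reaction periods under a vaccine not given at that dose |
|---|---|---|
| V1 error, SAP 3.3 applied in time | one product, not the assigned one | 0 of 3 |
| V1 error, protocol's general rule applied at V3 and V5 | mixed | 2 of 3 |
| V1 error found after the assigned product was given at V3 | mixed or not settled by the text | 1 or 2 of 3, depending on V5 |
| V1 correct, error at V3 only or V5 only | mixed | 1 of 3 |
| V1 correct, errors at both V3 and V5 | mixed | 2 of 3 |

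Following SAP 3.3 keeps the series to one product, but its V3 and V5 doses are then themselves unassigned. Following the protocol's general rule restores the assignment but mixes the series. One child cannot be dosed under both.

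**2. PP_IMM.** Three study vaccinations of different products satisfy the dose count. Whether such a child stays in depends on a case-by-case judgement, made on data pooled across arms (SAP 3.4), with no product criterion to apply. If PP_IMM takes the SAP's FIP grouping, a child given one wrong product throughout under SAP 3.3 is counted under a vaccine never received. If it takes the protocol's as-received grouping, that child is counted correctly, but a mixed series has no defined arm.

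**3. Scale for IgG.** Inputs: 220 per group with 10% non-evaluable, so n = 220 × 0.9 = 198; CV at most 1.5 (SAP 3.2.1); VAC-056 post-booster GMCs (Protocol Table 10).

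Plan's own figure: log SD = √ln(1 + 1.5²) = 1.0857. GMC bounds are exp(±1.96 × 1.0857/√198) = 0.860 and 1.163 (stated 0.86 and 1.16). Ratio bounds are exp(±1.96 × 1.0857 × √(2/198)) = 0.807 and 1.238 (stated 0.81 and 1.24). The log half-width of the ratio interval is 0.214.

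Suppose m of the 198 children in the PNEUMOSIL arm respond at the Synflorix level. The arm's GMC is then multiplied by exp(−m × ln R/198), where R is the VAC-056 GMC ratio.
- 6A: ln(4.87/0.42) = 2.45 and 2.45/198 = 0.0124. One child lowers the GMC by 1.2%, which is 0.0124/0.214 = 6% of the half-width. Five children lower it by 6.0%, which is 29% of the half-width.
- Type 1: ln 2.34 = 0.850 and 0.850/198 = 0.0043, or 0.4% per child.

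**4. Scale for opsonophagocytic (OPA) titers.** The subset is 50 per group, with 45 as the target minimum (SAP 3.5). VAC-056 post-booster 6A GMTs were 3063.37 and 44.98 (Protocol Table 11). ln(68.1)/45 = 0.094, so one child lowers the GMT by about 9%. The planned upper bound for a GMT ratio of 1 is 1.73, and ln 1.73 = 0.548, so this is 0.094/0.548 = 17% of the half-width.

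Items 3 and 4 describe a child with a full Synflorix-type response counted as PNEUMOSIL. They do not describe a mixed series. The number of errors is not in the documents; one and five are assumptions.

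**The case against.** Several objections have force.

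**The protocol text is general.** A reader might infer that the protocol contains a contrary instruction for children who had a V1 error. It does not. Its passages describe ordinary conduct, and the SAP adds an exception found nowhere else. What stands is that the protocol's wording, applied as written, gives a different product from SAP 3.3.

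**Site practice is unknown.** A reader might infer that dosing staff follow the protocol and never see the SAP rule. Neither document says so. Protocol 5.5 refers the detailed preparation and administration steps to the study-specific procedure, which may carry a post-error rule.

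**A PP_IMM safeguard exists.** Major deviations can be excluded in blind review, unassigned treatment is a named medication error, and SAP 4.2 requires all deviations to be reviewed, tabulated and listed. It would be wrong to say that nothing protects PP_IMM. The safeguard is discretionary, however, and does not reach the Safety Population.

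**As-received may be intended for PP_IMM.** The appendix limits the switch to randomized grouping to the supportive FIP analyses, so as-received is a natural reading for PP_IMM. It is still not written down.

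**V1 grouping is prespecified and has a use.** Both documents adopt it, and the summary across all three vaccinations needs one group per child. That supports keeping it for cumulative summaries. It does not justify per-dose tables that name a vaccine not given at that dose.

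**Conclusion.** The plan is wrong as written, on a limited scale. SAP 3.3 and the protocol's general rules lead to different products after the same V1 error and must be reconciled. The safety consequence follows directly from the V1 grouping rule: each mixed-series child has one or two of three solicited-reaction periods under the wrong vaccine. It would be too strong to say two of three for every allocation error, since a V1 error handled in time under SAP 3.3 misattributes none.

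For immunogenicity, misattribution is possible but not established, because blind review may remove the child and the PP_IMM grouping is unstated. A reader might take 1.2% per child as the effect of a mixed series on the 6A GMC. It is an upper illustration for IgG, because it assumes a full Synflorix response, the most extreme serotype, no exclusion, and VAC-056 values from three primary doses plus a booster rather than 2+1. A mixed series would probably shift the GMC less. The same assumptions lie behind the 9% for OPA.

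The documents report no allocation error. With none, the effect is nil. With a few, it is small for most serotypes.

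**What to change.** 1. Reconcile SAP 3.3 with Protocol 3, 5.5 and 7.1.2 so that one instruction applies in both documents, covering late detection and errors first made at V3 or V5. Which instruction applies is for the sponsor to decide.
2. In SAP 3.8, name a series of more than one product as a PP_IMM exclusion (all three doses for the Primary population, both primary doses for the Secondary), and state that PP_IMM is analysed by product received.
3. In SAP 5.4.3, tabulate per-dose solicited reactions by the product given at that dose. Keep the across-all-doses and overall TEAE summaries by V1 product, with mixed-series children flagged. State which rule the 28-day post-vaccination TEAE tables in SAP 5.4.2 follow.

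The cost is a few sentences in each document and a small change to table programming. No new data are needed: under Protocol 7.1.2 the unblinded site staff already keep a list of the vaccine assigned and the vaccine administered. The wording should be settled before final unblinding.
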